7.3.2 Study Procedures by Visit

Visits following the Baseline Visit are to occur at Months 1, 3, 6, 9, and 12 at Week 4, 12, 26, 39 and 52 (Final Visit). Interim study visits and the Final Month 12 (Week 52) study visit may be conducted (on an individual subject basis) up to 14 days before or after the regularly scheduled study visit. An unscheduled visit may occur in the event that the investigator determines that the subject should be seen for safety reasons.

7.3.2.1 Screening Visit

The following procedures will be performed during the Screening visit:

- Obtain subject's written informed consent prior to initiating any study procedures, including instructing the subject to discontinue use of medication that requires a washout (see Section 7.5.9.1). Provide subject with a copy of signed and dated consent form. Document subject's informed consent in the subject's medical record.
- Screen the potential subject according to the study inclusion/exclusion criteria.
- Schedule the Baseline/Day 1 visit to occur after the results of the laboratory safety testing are received and any required washout period is completed.
- Record Demographic information including age, sex, race, ethnicity and Fitzpatrick skin type (Appendix B)
- Record medical history. Include information on: subject's history of rosacea and any previous therapies, including:
 - The approximate date of physician's diagnosis of rosacea;
 - The subject reported signs and symptoms of rosacea,
 - How often they experience these symptoms?
 - Whether symptoms are continuous or occasional?
 - What, if anything, appears to trigger or worsen these symptoms?
 - sunlight
 - stress
 - alcohol
 - exercise
 - hot and cold temperatures
 - spicy food
 - Rosacea therapies within the previous 5 years.
- Review and record concomitant medications/therapies used in the last 30 days.
- Assess whether the subject will require a washout period
- Perform a limited Physical Exam (refer to Section 7.4.2) with vital signs, height and weight measurements.
- Obtain a blood sample for hematology and chemistry analysis.
- Perform an in-office urine pregnancy test on all females of childbearing potential.
- Perform the Investigators Global Assessment (IGA) of rosacea. **It is important that the same evaluator performs the evaluations for the same subject at each**

CONFIDENTIAL

Version Date: 07 March 2017

visit, however it may not be feasible in all instances. Every effort should be made to maintain consistency of the evaluator for each subject.

- Schedule the next visit.

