Currently, there is no cure for rosacea and the etiology is poorly understood.⁸ Many theories regarding the cause of rosacea have been highlighted in the literature. The pathology of rosacea may be multifactorial and has several associations still not well understood: abnormal vascular and immune system responses; proliferation of commensal mites seen in hair follicles, *Demodex folliculorum*; bacterial proliferation in the human gut of *Helicobacter pylori*; prolonged topical steroid use and other aggravating trigger factors like sun and stress.^{9,10} Gallo and his colleagues found an abnormally high level of the naturally occurring antimicrobial peptides known as cathelicidins upon histopathological staining of the skin of patients with rosacea.¹¹

CONFIDENTIAL

Version Date: 07 March 2017

Therapeutic approaches for the treatment of rosacea may be categorized by the subtype (1-4).⁵ For example, systemic treatments and ablative therapy are used for erythematotelangiectatic rosacea (Subtype 1). Surgery or laser therapy may be indicated for phymatous rosacea (Subtype 3). Topical or systemic medications may be prescribed for papulopustular and ocular rosacea (Subtype 2 and 4, respectively).

The inflammatory (papulopustular) lesions of rosacea affect both the sebaceous and hair follicles.¹² Inflammatory cells may be key pathophysiologic factors in the development of rosacea.¹³ Intrafollicular neutrophils have been observed in inflammatory rosacea and the proteases released by these neutrophils may degrade extracellular matrix macromolecules.¹⁴

There is no cure for rosacea and treatment is aimed at alleviating the symptoms. Topical or oral medications are generally prescribed for mild to moderate papulopustular rosacea. These topical medications include: metronidazole, azelaic acid, ivermectin, sodium sulfacetamide and sulfur, erythromycin, and tretinoin. Oral medications prescribed for severe disease include doxycycline at microbial and subantimicrobial doses, and minocycline.^{4, 15, 16, 17} Isotretinoin, although not FDA approved for the treatment of rosacea, has also been prescribed when other agents have failed. In particular, treatments for severe rosacea are inadequate, and isotretinoin use has occurred with increasing frequency in this patient population.^{18, 19, 20, 21, 22, 23} Hence, topical Omiganan has the potential to become an important addition to the dermatologist's armamentarium in treating severe rosacea.

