7.2.2 Exclusion Criteria

Subjects are not eligible to participate in the study if any of the following are present:

1. Subjects with clinically significant abnormal findings at the Screening or Baseline/Day 1 Visit that would require a new intervention or treatment or a change in treatment that would in the opinion of the investigator supersede participation in the clinical trial.
2. Subjects with steroid rosacea or subtype 3 (phymatous rosacea).
3. Subjects with nodular rosacea (defined as more than 2 lesions greater than 5 mm).
4. Subjects with underlying diseases or other dermatological conditions, such as; atopic dermatitis, perioral dermatitis, or seborrheic dermatitis, which requires the use of interfering topical or systemic therapy or may interfere with the rosacea diagnosis or its assessment.
5. Subjects with known allergies to the active ingredient or any of the excipients. (See Section 7.5.2)
6. Subjects who have not undergone the specified washout period(s) for the following topical preparations applied to the face or subjects who require the concomitant use of any of the following topical preparations/treatments applied to the face:

Product Washout Period
(Prior to Baseline/First Dose)

- Abradants, astringents, toners, facials, masks, or moisturizers containing retinols, AHA (alpha hydroxyl acids), salicylic acids
 - Tanning booths/beds 1 week
 - Antibiotics (other than topical ocular application) 2 weeks
 - Antimicrobial soaps 2 weeks
 - Corticosteroids 2 weeks
 - Other anti-inflammatories 2 weeks
 - Other rosacea treatments (e.g., azelaic acid, metronidazole, ivermectin, sulfacetamide) 2 weeks
 - Retinoids 4 weeks
7. Subjects who have not undergone the specified washout period(s) for the following systemic treatments or subjects who require the concomitant use of any of the following systemic treatments:

Product Washout Period
(Prior to Baseline/First Dose)

- Antibiotics 4 weeks
 - Corticosteroids 4 weeks
 - Retinoids 4 weeks
8. Female subjects who are pregnant, nursing, or planning a pregnancy within the study period.
9. Subjects using an investigational drug within 30 days of the Baseline Visit or who are currently participating in an investigational study. Use of an investigational drug/device and/or participation in another investigational study is prohibited during this study.
10. Subjects who currently abuse alcohol or drugs or who have a history of chronic alcohol or drug abuse with in the past year.

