7.3 CONDUCT OF STUDY

7.3.1 Table of Study Procedures

Procedures	Screening (Within 30 days of Baseline)	Baseline (Day 1)	Interim Visits: Month 1, 3, 6, and 9 (Week 4, 12, 26 and 39 ± 14 days) or Unscheduled Visit	Final Visit: Month 12/EOT (Week 52 ± 14 days)
Informed Consent	X			
Demographics, Medical and Rosacea History	X	X		
Limited Physical Exam including weight	X (including height)			X
Vital signs	X		X (Month 6 only)	X
Blood collection for Clinical Laboratory Test (hematology, chemistry)	X			X
Blood collection for immunogenicity testing		X	X	X
Urine Pregnancy Test, if applicable	X			X
Investigator Global Assessment	X	X	X	X
Inclusion/Exclusion Criteria	X	X		
Weigh Tubes/Dispense Study Drug		X	X	
Dispense Diaries		X	X	
Collect Diaries			X	X
Instruct on Treatment Application		X	X	
Apply Study Drug		X	X	X
Collect drug/ Drug Accountability/ Compliance check			X	X
Previous/Concomitant Medication/Therapy Review	X	X	X	X
Adverse Event Assessment		X ¹	X	X

¹ Adverse event assessment during the Baseline visit will be performed following the first application of study drug.

CONFIDENTIAL

Version Date: 07 March 2017

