7.4.4 Clinical Laboratory Testing

Blood samples (approximately 11 mL) will be collected at Screening and the Month 12 Visit (Early Termination, or Final/EOT Visit), for hematology and chemistry laboratory analysis (total expected volume of approximately 22 mL). A central laboratory will perform the sample analysis for all study sites. Instructions for sample collection, preparation, labeling, and shipping will be provided by the laboratory.

All laboratory values that are considered clinically significant will be reported as an adverse event and followed as such. The following parameters will be determined:

- Hematology: Complete blood count (CBC), including hemoglobin, hematocrit, red blood cell (RBC), white blood cell (WBC), count with differential, and platelet count.
- Blood Chemistry/Lipids: sodium, potassium chloride, bicarbonate or carbon dioxide, glucose, blood urea nitrogen (BUN), creatinine, calcium, uric acid, total bilirubin, total protein, albumin, aspartate aminotransferase (AST), alanine aminotransferase (ALT), alkaline phosphatase, gamma glutamyl transferase (GGT), total cholesterol, high-density lipoproteins (HDL), low-density lipoproteins (LDL), triglycerides, and lactic dehydrogenase (LDH).

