#### **5.1 Baseline and Follow-Up Visits**

Visits and timepoints for all analyses will be as record on the eCRFs. Baseline will be the later of the non-missing values from the Screening and Baseline/Day 1 visits scheduled to occur prior to receiving study medication.

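### For subjects on, or recently off, a washout-listed systemic drug at Screening, lab changes and shifts mix stopping that drug with omiganan exposure

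*Protocol*

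**What the plan says.** **Lab timing.** Protocol 7.4.4 says the samples "will be collected at Screening and the Month 12 Visit (Early Termination, or Final/EOT Visit), for hematology and chemistry laboratory analysis". The table in Protocol 7.3.1 agrees, with marks at Screening and the Final Visit only. At the Baseline Visit (Protocol 7.3.2.2) the Screening results are reviewed, and the only blood drawn is for immunogenicity.

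**Washout timing.** In Protocol 7.3.2.1 consent comes before study procedures, "including instructing the subject to discontinue use of medication that requires a washout". The same visit includes the instruction "Obtain a blood sample for hematology and chemistry analysis". Day 1 is booked for after the lab results are in and any washout is finished.

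**Drugs concerned.** Protocol 7.2.2 excludes "Subjects who have not undergone the specified washout period(s) for the following systemic treatments" and sets 4 weeks each for antibiotics, corticosteroids and retinoids. Protocol 7.5.9.1 bars the same drugs during treatment.

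**Analysis.** SAP 5.1 states: "Baseline will be the later of the non-missing values from the Screening and Baseline/Day 1 visits". SAP 4.3.2 plans lab change summaries and shift tables, with no split by washout status. SAP 5.3 confines unscheduled results to listings.

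**The concern.** Long-term safety is the trial's only objective, there is one treatment arm, and each subject has one scheduled lab after baseline. A change from Screening to the final visit is naturally read as a change on omiganan. For a subject who stops a systemic drug between the Screening sample and Day 1, it is also a change off that drug.

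Such subjects can be expected. The trial enrols severe disease, and Protocol 5.1 says that oral doxycycline and minocycline are prescribed for severe disease and that "isotretinoin use has occurred with increasing frequency in this patient population". The panel in Protocol 7.4.4 covers lipids, liver enzymes, glucose and white cells. If one of these drugs had moved an analyte, the planned tables could not tell its withdrawal from an effect of the gel.

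**Working it through.** The plan states no figure to reproduce: the study is descriptive and its size rests on exposure targets (Protocol 7.6.1 and 7.6.2). The check covers the timing and then the form of the bias.

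**1. Which lab value is the baseline?** The candidates under SAP 5.1 are Screening and Day 1. No safety lab is scheduled at Day 1, so the rule returns the Screening value. An unscheduled repeat after washout would be listed but would not enter the summaries (SAP 5.3).

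**2. Is that value before washout?** The screening window is 30 days (Protocol 7.3.1). The systemic washout is 4 × 7 = 28 days (Protocol 7.2.2). The slack is 30 − 28 = 2 days. A subject who stops at Screening and completes 4 weeks must be screened between Day −30 and Day −28, so the baseline lab reflects a drug still in use or stopped at most about 2 days before. A subject who had already stopped 14 days earlier is partly washed out. A subject on none of these drugs, or already past the washout period, is unaffected.

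**3. Form of the bias.** Let *D* be the mean lab change due to omiganan, *f* the share of subjects on or recently off a listed systemic drug at Screening, and *w* the mean lab effect of stopping it in those subjects. Then

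expected mean change = *D* + *f* × *w*.

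- If the prior drug raised the analyte, *w* is negative and a rise on omiganan can be hidden.
- If it lowered the analyte, *w* is positive and a false rise can appear.
- If *f* = 0, the extra term is zero.

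With *q* the chance that stopping the drug moves a value across a normal limit, in either direction, spurious shifts = *N* × *f* × *q*.

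**4. Illustration only.** The documents give none of *f*, *w* or *q*. The values below are assumptions: *f* from 5% to 30%, *q* from 10% to 30%.

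| Assumed *f* | Affected of 300 | Affected of 100 | Bias in mean change | Spurious shifts per 100 (*q* = 10% to 30%) | Spurious shifts per 300 |
|---|---|---|---|---|---|
| 0% | 0 | 0 | 0 | 0 | 0 |
| 5% | 15 | 5 | 0.05*w* | 0.5 to 1.5 | 1.5 to 4.5 |
| 10% | 30 | 10 | 0.10*w* | 1 to 3 | 3 to 9 |
| 20% | 60 | 20 | 0.20*w* | 2 to 6 | 6 to 18 |
| 30% | 90 | 30 | 0.30*w* | 3 to 9 | 9 to 27 |

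For example, 100 × 0.05 × 0.10 = 0.5 and 300 × 0.30 × 0.30 = 27. The table shows how the answer depends on the inputs; it does not estimate this trial's bias.

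**5. Can affected subjects be identified?** Medications used in the 30 days before Screening are recorded (Protocol 7.3.2.1), which spans the 28-day washout. Washout medications are also recorded (Protocol 7.5.9). That section does not say that stop dates are captured.

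**The case against.** **The tables are not the only lab evidence.** A reader might infer that they are. Protocol 7.4.4 has every clinically significant lab value reported and followed as an adverse event, whatever the shift table shows. This stands: a clinically important late abnormality would still be captured.

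**The direction is not established.** A reader might infer that the bias flatters omiganan, because a prior drug may have raised the baseline. The documents give no lab effect for any washed-out drug, and *w* can take either sign, by drug and by analyte. That a value abnormal at baseline cannot become newly abnormal is true of any shift table. This stands: the plan supports confounding, not a favourable bias.

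**The affected group may be small.** Subjects must be healthy. Those who need the listed systemic drugs, or whose chronic condition may call for them, are excluded (Protocol 7.2.1 and 7.2.2). Nor does every subject needing washout have a fully on-drug baseline. The background on isotretinoin gives no share for this trial. This stands, and it is why no size can be claimed.

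**Systemic lab effects of omiganan may be unlikely.** Protocol 5.1 reports no systemic absorption at gel strengths of 0.5% to 3%, including a 21-day maximum-use study in 26 subjects. This lowers the priority. It does not make the change and shift tables interpretable in affected subjects, and the sponsor plans to present those tables for up to 12 months of use.

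**Conclusion.** The concern holds as a conditional limit on interpretation. The order of events is clear from the documents: Screening lab, washout, Day 1 without a safety lab, then a final lab planned to be off the washed-out drugs. In subjects on or recently off a listed systemic drug at Screening, lab change and shift cannot be attributed to omiganan alone, and a single-arm study has no control group to separate the two effects.

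The size cannot be computed. It is *f* × *w* for mean change and *N* × *f* × *q* for shifts, with all of *f*, *w* and *q* missing from the documents; at *f* = 0 there is no bias. Expressing it in standard errors would add further assumptions and would serve little purpose where no test is planned. This is a cheap improvement to make before the lab tables are produced. It does not undermine the safety evaluation as a whole.

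**What to change.** In SAP 5.1, define a flag for subjects whose Screening lab was taken while on, or within the 4-week washout period of, a systemic antibiotic, corticosteroid or retinoid, using the recorded prior and washout medications. Confirm that the eCRF captures stop dates for these medications, since the flag depends on them, and state how a missing date is handled.

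In SAP 4.3.2, keep the all-treated lab change and shift tables as the main display, in line with SAP 4.2. Add the same tables without flagged subjects as a supportive analysis, and report the number flagged, which supplies the missing *f*.

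The cost is one derived variable and a repeat of existing tables, with no added visit or blood draw. The supportive tables have a smaller n, and unflagged subjects may differ from flagged ones in other ways, so a difference between the two sets is not purely a washout effect. Flagged subjects still have no post-washout lab baseline, and no reanalysis can supply one.

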7.3.2.2 Baseline Visit (within 30 days of Screening)

- Review the study inclusion/exclusion criteria to confirm eligibility, including review of the laboratory results for any clinically significant findings that would exclude the subject from eligibility for the study.
- Review and record any changes since the first visit in medications/therapies, and the subject's health.
- Obtain a blood sample for immunogenicity testing
- Perform the Investigators Global Assessment (IGA) of rosacea. **Every effort should be made to maintain consistency of the evaluator for each subject.**
- If the subject has fulfilled the eligibility requirements, as stated in the inclusion/exclusion criteria, provide the subject four tubes of omiganan topical gel. Record the subject number and dispensing date on the tubes that are assigned to that subject. Record the dispense date and the subject number on the source document.
- First Treatment Application –
 - Weigh the tubes that are designated to be dispensed to the subject prior to the subject applying their first dose of study medication. The tubes should be weighed with the cap on as outlines in section 7.5.7.
 - Give the subject a copy of the treatment application instructions (see Appendix A) and allow the subject take time to read them. Provide instruction to the subject on the daily application of study drug and confirm the subjects understanding of the instructions.
 - Record the Subject # and date of dispensing on the tube labels and dispense the tubes to the subject.
 - The subject should be instructed to apply the treatment once daily, preferably each morning, at approximately the same time for the duration of the study. A thin layer of the assigned study drug (approximately 0.4 gm) should be applied to the subject's face, including the non-affected areas (as described in Appendix A). The subject should be reminded to use all of the contents of one tube before they start using a new tube from their dispensed supply
 - Under the supervision of the study coordinator or designee, the subject should apply the first dose of study drug at the study site and the observer should observe that the subject applies a thin layer to the entire face as per the treatment application instructions (see Appendix A).
- Instruct the subject on the use of the daily diary and dispense the diary.

CONFIDENTIAL

Version Date: 07 March 2017

Have the subject record the first application of study drug in the diary during the site visit and confirm their understanding of the use of the diary.

After the first application of study drug at this visit -

- Observe the subject for any immediate adverse events.
- Remind the subject about restricted therapies (see Section 7.5.9.1).
- Remind the subject to contact the investigator if he/she experiences any adverse events.
- Remind the subject that the study drug tubes are not to be discarded and that the drug tubes must be returned to the site at the next study visit. Subjects should be instructed to immediately report lost tubes to the site.
- Remind the subject to apply the study drug once daily, as directed, preferably in the morning.
- Remind the subject to record their study drug application in the diary each day during the study and to use the gel from one tube before opening a new tube.
- Remind the subject to return the diary to the site at the next study visit.
- Remind the subject to follow the treatment application instructions.
- Schedule the next visit.

7.3.2.3 Interim Visits at Months 1, 3, 6, and 9 (Weeks 4, 12, 26 and 39 ± 14 days)

- Question the subject and record any new or changes in adverse events.
- Question the subject about any new or changes in concomitant medications/therapies.
- Obtain a blood sample for immunogenicity testing
- Perform the Investigators Global Assessment (IGA) of rosacea. **Every effort should be made to maintain consistency of the evaluator for each subject.**
- Vital signs will be measured (Month 6 Visit ONLY)
- The subject should apply the study drug at the study site under supervision of appropriate site personnel
- **Treatment Compliance Check** - Collect the study diary to perform a treatment application compliance review. Check compliance by reviewing the number of treatment applications in the diary to determine if there are missed doses. The subject should be re-instructed on study drug application, if compliance is an issue.
- **Dispensing and Return of Study Treatment** - No new study drug supply will be dispensed at the Month 1 visit; the drug tubes which were dispensed to the subject at Baseline should be returned to them at the Month 1 Visit after completing the treatment application check (unless the tube is empty; then it should be retained at the site and weighed). Record the date of dispensing and subject number on each tube label. **Weigh returned tubes.** The dispensing and return information should be recorded on the source document. Collect the previous diary and dispense a new diary to the subject at the Month 1, 3, 6, and 9 Visits. The diary should be collected at each visit.
- Remind the subject about restricted therapies (see Section 7.5.9.1).

CONFIDENTIAL

Version Date: 07 March 2017

- Remind the subject to apply the study drug once daily, as directed, and record their daily treatment application in their diary.
- Remind the subject to contact the investigator if he/she experiences any adverse events.
- Remind subject that the study medication tubes are not to be discarded and all must be returned to the site at the next study visit. Remind them to notify the site immediately if they have lost a tube.
- Remind the subject to return the diary to the site at the next study visit.
- Remind the subject to follow the treatment application instructions.
- Schedule the next visit

7.3.2.4 Final Treatment Visit at Month 12/End of Treatment Visit (Week 52 ± 14 days/EOT Visit)

- Question the subject and record any new or changes in adverse events.
- Question the subject and record any changes or additions to concomitant medications/therapies.
- Perform the Investigators Global Assessment (IGA) of rosacea. **Every effort should be made to maintain consistency of the evaluator for each subject.**
- Perform a limited Physical Exam with vital signs, and weight measurement
- **Obtain a blood sample for immunogenicity testing**
- Obtain a blood sample for hematology and chemistry analysis
- Perform an in-office urine pregnancy test on all females of child-bearing potential.
- The subject should apply the study drug at the study site under supervision of appropriate site personnel
- **Treatment Compliance Check** - Collect the study drug tubes and diary to perform a treatment application compliance review. Check compliance by reviewing the number of treatment applications in the diary to determine if there were any missed doses. All study drug tubes should be collected by the last study visit. The weight of the tubes at dispensing and return should be documented. Any missing tubes must be documented.

